6.4.1 Return and/or destruction of treatments

A detailed treatment log of the destroyed IMP will be established with the Investigator (or the pharmacist) and countersigned by the Investigator and the monitoring team. The Investigator will not destroy the used and unused IMP unless the Sponsor provides written authorization. For NIMP reimbursed by the Sponsor, tracking and reconciliation will be achieved by the Investigator (or the pharmacist, if appropriate) as per local requirements.

Sharp containers containing all used PFSs will be brought back to the site by the study participant for the purpose of destruction.

Destruction is strongly encouraged at site level, nevertheless, if the site is not able to destroy or destruction is not allowed in the country, all treatments kits will be retrieved by the Sponsor.

6.5 CONCOMITANT THERAPY

The following treatments are prohibited during the study (including during screening period and the 30 weeks of the treatment period):

- Initiation of any antidiabetic agents, other than the IMP, or increase in dose of preexisting OAD(s), before pre-rescue assessments and initiation of rescue therapy (short-term use [<10 consecutive days] of short-acting insulin for treatment of acute illness or surgery is allowed)
- Initiation of any GLP-1 RAs (eg, exenatide, liraglutide, dulaglutide, or semaglutide) and DPP-4 inhibitors (eg, sitagliptin, saxagliptin, vildagliptin, or linagliptin)
- Initiation of any prescription weight-loss drugs (eg, phentermine, lorcaserin, or orlistat)
- Gastric surgery or other gastric procedures for weight loss
- Systemic use of glucocorticoids for more than 10 consecutive days (topical, nasal spray, inhaled, or intra-articular applications are allowed)
- Any investigational drug other than IMP for this study

Glucagon-like peptide-1 receptor agonists are known to decelerate gastric emptying. The delay of gastric emptying may impact absorption of concomitantly administered oral medicinal products. As drug-drug interaction data are not yet available for efpeglenatide, caution should be exercised. Drug levels of oral medications with narrow therapeutic index should be adequately monitored.

Any medication or vaccine (including over-the-counter or prescription medicines, vitamins, and/or herbal supplements) that the participant is receiving at the time of enrollment or receives during the study must be recorded along with:

- Reason for use
- Dates of administration including start and end dates
- Dosage information including dose and frequency

6.6 DOSE MODIFICATION

Up-titration of IMP from randomization to Week 4 is described in [Table 2](#). From Week 4 (Visit 5) through the rest of the double-blind treatment period, participants will remain on the randomized IMP (efpeglenatide assigned dose or placebo) until the EOT at Week 30 (Visit 12).

6.7 INTERVENTION AFTER THE END OF THE STUDY

The IMPs will not be provided after the end of the treatment period.

When a participant's participation in the trial ends, the participant will consult with his/her Investigator to decide on the best available treatment.

7 DISCONTINUATION OF STUDY INTERVENTION AND PARTICIPANT DISCONTINUATION/WITHDRAWAL

Withdrawal of consent for treatment should be distinguished from (additional) withdrawal of consent for follow-up visits and from withdrawal of consent for non-participant contact follow-up (eg, medical record checks). The site should document any case of withdrawal of consent.

7.1 DISCONTINUATION OF STUDY INTERVENTION

The IMP should be continued whenever possible.

In case the IMP is stopped, it should be determined whether the stop can be made temporarily; permanent IMP discontinuation should be a last resort. Any IMP discontinuation must be fully documented in the eCRF. In any case, the participant should remain in the study as long as possible to collect endpoint data at Week 30 vital safety status at the scheduled end of study.

7.1.1 Permanent discontinuation

Permanent IMP discontinuation is any IMP discontinuation associated with the definitive decision from the Investigator not to re-expose the participant to the IMP at any time during the study, or from the participant not to be re-exposed to the IMP whatever the reason.

The participants may withdraw from treatment with IMP if they decide to do so, at any time, and irrespective of the reason. Participants should discuss stopping the IMP with the site before doing so in order that questions can be addressed, concomitant therapy can be adjusted if needed, and a follow-up assessment arranged. All efforts should be made to document the reasons for treatment discontinuation and this should be documented in the eCRF.

A participant should withdraw from treatment with IMP in case of the following:

- Intercurrent conditions that require discontinuation of IMP: eg, laboratory abnormalities (see decision tree and general guidance for the follow-up of laboratory abnormalities in Appendix 6 [[Section 10.5](#)]), diagnosis of acute pancreatitis confirmed by gastroenterologic evaluation and imaging, unless a clear cause unrelated to IMP is confirmed and the participant has recovered from pancreatitis (see Appendix 7 [[Section 10.5.2](#)]), or calcitonin value ≥ 50 pg/mL (see Appendix 7 [[Section 10.5.3](#)]).
- If, in the Investigator's opinion, continuation with the administration of IMP would be detrimental to the participant's well-being
- Pregnancy (in female participants)
- Confirmed intolerance to the allocated dose of IMP
- Any code breaking requested by the Investigator
- At the specific request of the Sponsor

As all data until the scheduled date of study completion will be used in statistical analyses, it is important to collect data for all participants, under treatment or not, during the 30 weeks of the study. A high rate of missing data could jeopardize efficacy results of the study. Refer to the SoA ([Section 1.3](#)) for data to be collected at the time of IMP discontinuation and follow-up and for any further evaluations that need to be completed.

Any abnormal laboratory value or ECG parameter will be immediately rechecked for confirmation (as soon as possible, preferably within 24 hours) before making a decision of permanent discontinuation of the IMP for the concerned participant.

Handling of participants after permanent intervention discontinuation

Every effort should be made to maintain participants in the study. Participants will be followed according to the study procedures specified in this protocol up to the scheduled date of study completion, or up to recovery or stabilization of any AE to be followed as specified in this protocol, whichever comes last.

If possible, the participants will be assessed using the procedure normally planned for the EOT Visit, including a PK sample if this visit can be scheduled 6 to 7 days after the permanent discontinuation of IMP. For participants who discontinue IMP but remain in the study, the remaining visits should occur as scheduled where possible. The Investigators should discuss with the key visits to attend. All efforts should be made to continue to follow the participants for primary and secondary endpoints, after the discontinuation of IMP.

The value of all their study data collected during their continued involvement will be emphasized as important to the public health value of the study. Participants who withdraw from the study IMP should be explicitly asked about the contribution of possible AEs to their decision and any AE information elicited must be documented.

All cases of permanent study IMP discontinuation must be recorded by the Investigator in the appropriate pages of the eCRF when considered as confirmed.

7.1.2 Temporary discontinuation

Temporary IMP discontinuation corresponds to at least 1 (one) dose not administered to the participants.

All IMP discontinuation should initially be considered as temporary unless permanent discontinuation is mandated by the protocol (see [Section 7.1](#)), and the Investigator should make best effort to resume IMP treatment as early as practically possible. There is no defined limit to the duration of temporary discontinuation.

Temporary IMP discontinuation may be considered by the Investigator because of suspected AEs (including intolerance to IMP planned dose). For all temporary IMP discontinuations, duration should be recorded by the Investigator in the appropriate pages of the eCRF.

7.1.3 Rechallenge

Reinitiation of treatment with the IMP will be done under close and appropriate clinical/and or laboratory monitoring once the Investigator will have considered according to his/her best medical judgment that it is safe for the participant to restart the IMP. In case of IMP intolerance, a one-time rechallenge is recommended following temporary discontinuation before deciding to permanently discontinue the IMP. If a maximum of 2 consecutive doses are missed, the IMP can be restarted with the last dose given. In cases where 3 or more consecutive doses are missed, the titration should be reinitiated.

Participants who temporarily discontinue IMP should be reassessed at every visit to determine whether it is possible to safely resume IMP. If a decision has been made that the discontinuation is permanent, then the participant should be considered as permanently discontinued and the corresponding eCRF page should be completed. Please note that permanent discontinuation should be a last resort.

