4.3 JUSTIFICATION FOR DOSE

The selection of efpeglenatide 2, 4, and 6 mg once weekly doses is based on the results of early phase studies.

Efpeglenatide has shown increasing efficacy up to the highest dose tested. Both once-weekly 2 mg and 4 mg doses have shown clinically relevant efficacy in study HM-EXC-203. The achieved HbA1c reduction indicates that the dose-response plateau has not been reached with the 4 mg dose so most likely, higher efficacy of the 6 mg dose compared to the 4 mg dose can also be expected for glycemic control in diabetic patients. The once-weekly 6 mg dose tested in non-diabetic subjects in the Phase 2 study (HM-EXC-205) has shown higher efficacy in the decrease of body weight than the once-weekly 4 mg dose in this population.

Nausea and vomiting events appeared to be dose-related and the trend over time showed an increase in incidence after the first injection with a general decrease thereafter for all tested doses. Based on the observed general decrease of GI events incidence after the first week of treatment with efpeglenatide, dose increases to achieve the higher doses of 4 and 6 mg (in the corresponding arm) will be in 2 mg step intervals every 2 weeks in order to minimize the GI adverse effects. The escalation step of 2 mg is small enough to contribute to improvement of GI tolerability at dose increase. With this dose escalation schedule, the dose of 4 mg once-weekly will be achieved 2 weeks after the first dose of efpeglenatide and the maximal dose of 6 mg once-weekly will be achieved only 4 weeks after the first dose of efpeglenatide.

Please refer to the IB for more details (2).

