Dosing instructions	
The injection interval of the IMP is once weekly on the same week day (eg, each Monday) at any time of the day. Injections should be administered SC to the abdomen, thigh or upper arm. For each injection, the date, time, and region of administration should be recorded. Within any selected region, the site of injection should be changed (rotated) at each administration to prevent skin reactions.
 
For selected visits during the treatment period up to Week 30 (corresponding to predose PK sample collection), the weekly dose will be administered at the site after blood sample collection (see SoA, Section 1.3).
 
For the other weekly administrations, if a dose is missed, participants must be instructed to administer it as soon as possible, if there are at least 3 days (72 hours) until the next scheduled dose. If less than 3 days remain before the next scheduled dose, participants should skip the missed dose and administer the next dose on the regularly scheduled day. In each case, participants should then resume their regular once weekly dosing schedule. The day of weekly administration can be changed if necessary as long as the last dose was administered 3 or more days before.
 
Predose PK samples are expected to be collected at least 6 to 7 days after the last dose of IMP. The corresponding study visits (Visit 5, Visit 8, Visit 10, and Visit 11) and the timing of dose administration before each of these visits should be scheduled to ensure, as much as possible, the duration of 6 to 7 days between them is maintained.
 
IMP dose schedule
 
  
 	Dose 1	Dose 2	Dose 3	Dose 4	Dose 5	
 
 	Day 1	Week 1	Week 2	Week 3	Week 4	
 
 	Visit 3		Visit 4		Visit 5	
 
 Dosing	(on-site)	(at home)	(on-site)	(at home)	(on-site)	
   
 Efpeglenatide 2 mg	2 mg	2 mg	2 mg	2 mg	2 mg	
 
 Efpeglenatide 4 mg	2 mg	2 mg	4 mg	4 mg	4 mg	
 
 Efpeglenatide 6 mg	2 mg	2 mg	4 mg	4 mg	6 mg	
 
 Placebo	Placebo	Placebo	Placebo	Placebo	Placebo	
  
 
From Week 4 (Visit 5) through the rest of the double-blind treatment period, participants will remain on the randomized IMP dose or placebo until the EOT at Week 30.
			Dose 1	Dose 2	Dose 3	Dose 4	Dose 5		Day 1	Week 1	Week 2	Week 3	Week 4		Visit 3		Visit 4		Visit 5	Dosing	(on-site)	(at home)	(on-site)	(at home)	(on-site)	Efpeglenatide 2 mg	2 mg	2 mg	2 mg	2 mg	2 mg	Efpeglenatide 4 mg	2 mg	2 mg	4 mg	4 mg	4 mg	Efpeglenatide 6 mg	2 mg	2 mg	4 mg	4 mg	6 mg	Placebo	Placebo	Placebo	Placebo	Placebo	Placebo

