	Dose 1	Dose 2	Dose 3	Dose 4	Dose 5																																													
	Day 1	Week 1	Week 2	Week 3	Week 4																																													
	Visit 3		Visit 4		Visit 5																																													
Dosing	(on-site)	(at home)	(on-site)	(at home)	(on-site)																																													
Efpeglenatide 2 mg	2 mg	2 mg	2 mg	2 mg	2 mg																																													
Efpeglenatide 4 mg	2 mg	2 mg	4 mg	4 mg	4 mg																																													
Efpeglenatide 6 mg	2 mg	2 mg	4 mg	4 mg	6 mg																																													
Placebo	Placebo	Placebo	Placebo	Placebo	Placebo																																													
Storage conditions	Store between +2°C and +8°C (36°F and 46°F). Do not freeze, protect from light.																																																	
Packaging and labeling	IMP will be provided in boxes in accordance with the administration schedule. The content of the labeling is in accordance with the local regulatory specifications and requirements.																																																	

The details of this table are specific to IMP; information of non-IMP is described separately in this section.

EOT: end of treatment; IMP: investigational medicinal product; NA: not applicable; PFS: prefilled syringe; PK, pharmacokinetic; SC: subcutaneous; SoA, Schedule of Activities.

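### For doses missed during titration, Table 2, Section 6.6 and Section 7.1.3 lead to different doses, and nothing says which governs

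*Protocol*

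**What the plan says.** Protocol Section 6.1, Table 2, sets doses by calendar week. The top-dose row reads "Efpeglenatide 6 mg 2 mg 2 mg 4 mg 4 mg 6 mg", for Day 1 and Weeks 1, 2, 3 and 4. The 4 mg arm takes 2, 2, 4, 4, 4 mg and the 2 mg arm takes 2 mg throughout. A missed dose is taken late if at least 3 days remain before the next one; otherwise "participants should skip the missed dose and administer the next dose on the regularly scheduled day". Table 2 then adds: "In each case, participants should then resume their regular once weekly dosing schedule". From Week 4, "participants will remain on the randomized IMP dose or placebo until the EOT at Week 30".

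Section 6.6 points to Table 2 for the up-titration and continues: "From Week 4 (Visit 5) through the rest of the double-blind treatment period, participants will remain on the randomized IMP", that is, on the assigned dose or placebo. It states no exception.

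Section 7.1.2 defines an interruption broadly: "Temporary IMP discontinuation corresponds to at least 1 (one) dose not administered to the participants". Section 7.1.3 gives the restart rule: "If a maximum of 2 consecutive doses are missed, the IMP can be restarted with the last dose given". After three or more consecutive missed doses, titration should be started again.

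Section 4.3 explains the escalation: dose increases "will be in 2 mg step intervals every 2 weeks in order to minimize the GI adverse effects".

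**The concern.** Under Section 7.1.2, a single dose skipped during titration is a temporary discontinuation as well as a missed dose under Table 2. Two instructions then apply to the same event. One returns the participant to a schedule in which the week fixes the dose; the other goes back to the last dose actually taken. While the dose is still rising, these need not agree. Neither place refers to the other, and Section 7.1.3 does not say how escalation continues after a restart at a lower dose.

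Sections 2.3 and 4.3 rely on gradual escalation to limit nausea and vomiting, which they describe as apparently dose related. If sites follow different sections, participants in the same arm with the same missed doses could receive different doses. That bears on tolerability and on how adverse events by arm are read. Sites cannot settle it themselves by picking a strength: syringes and kits are indistinguishable (Section 6.3.1), and an investigator who breaks the code must withdraw the participant from study drug (Section 6.3.2).

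**Working it through.** This is a trace of the schedule, not a statistical calculation.

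**Inputs.** Table 2 doses at Day 1 and Weeks 1 to 4: 2, 2, 4, 4, 6 mg (6 mg arm); 2, 2, 4, 4, 4 mg (4 mg arm); 2 mg throughout (2 mg arm). Planned step: 2 mg every 2 weeks (Section 4.3). No missed dose is taken late under the 3-day rule.

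**Plan's own figure.** With no missed doses, the 6 mg arm rises by 4 − 2 = 2 mg at Week 2 and 6 − 4 = 2 mg at Week 4. This matches Section 4.3: 4 mg after 2 weeks and 6 mg after 4 weeks.

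**Rules applied.** Table 2: the next dose is the one scheduled for that week. Section 7.1.3: after one or two missed doses, the next dose equals the last one given.

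| Arm | Missed | Last given | Next due | Table 2 | Section 7.1.3 |
|---|---|---|---|---|---|
| 6 mg | Week 1 | 2 mg | Week 2 | 4 mg | 2 mg |
| 6 mg | Week 2 | 2 mg | Week 3 | 4 mg | 2 mg |
| 6 mg | Week 3 | 4 mg | Week 4 | 6 mg | 4 mg |
| 6 mg | Weeks 1-2 | 2 mg | Week 3 | 4 mg | 2 mg |
| 6 mg | Weeks 2-3 | 2 mg | Week 4 | 6 mg | 2 mg |
| 4 mg | Week 1 | 2 mg | Week 2 | 4 mg | 2 mg |
| 4 mg | Week 2 | 2 mg | Week 3 | 4 mg | 2 mg |
| 4 mg | Week 3 | 4 mg | Week 4 | 4 mg | 4 mg |
| 4 mg | Weeks 1-2 | 2 mg | Week 3 | 4 mg | 2 mg |
| 4 mg | Weeks 2-3 | 2 mg | Week 4 | 4 mg | 2 mg |

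In the 2 mg arm both rules give 2 mg for every such gap.

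**Step size.** For Weeks 2-3 in the 6 mg arm, the Table 2 route is a step of 6 − 2 = 4 mg, twice the planned 2 mg. No other gap of one or two doses exceeds a 2 mg step.

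**Three missed doses.** In the 6 mg arm with Weeks 1-3 missed, titration restarted at Week 4 gives 2, 2, 4, 4, 6 mg at Weeks 4, 5, 6, 7, 8. The first 6 mg dose comes at Week 4 + 4 = Week 8, against Week 4 in Table 2 and Section 6.6.

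**Edge of the rule.** Table 2 applies its missed-dose text to administrations other than the predose PK visits (Visits 5, 8, 10 and 11). Weeks 1 to 3 are therefore covered. Week 4 is Visit 5 and may not be, so gaps that include Week 4 are left out of the table; there Section 6.6 alone points to the randomized dose.

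**The case against.** The best defence is to read the sections as rule and exception. Table 2's missed-dose text is about timing, speaks of one dose, and names no mg. Section 6.6 describes the planned regimen. Section 7.1.3 deals expressly with consecutive missed doses and with intolerance, under investigator judgment and close monitoring, and its wording for one or two missed doses is permissive. The Week 4 dose is given on site.

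Much of this stands. For two or more consecutive misses the reading is plausible, and the conflict is between two applicable instructions, not two strict orders. It does not settle the single missed dose, which Section 7.1.2 places under both rules. Nor does any text make Section 7.1.3 an exception to Section 6.6, although re-titration after three misses during Weeks 1 to 3 cannot meet the Week 4 statement.

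Several stronger readings are tempting but unsupported:

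- **Table 2 orders a move from 2 mg to 6 mg.** It does not say so; that dose follows only from combining the timing text with the week-indexed schedule.
- **Every missed dose in Weeks 1 to 3 is affected, in all 160 + 160 = 320 participants planned for the 4 and 6 mg arms.** In the 4 mg arm, Week 3 missed alone gives the same dose under both rules, and 320 is simply the size of two arms.
- **The conflict falls mainly on participants with early GI intolerance.** This is conceivable, but no data on missed doses are given, and Section 7.1.3 addresses intolerance directly.
- **The IRT allocates kits by calendar week.** Table 2 says only that boxes follow the administration schedule; the allocation logic is not described.

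**Conclusion.** The three places lead to different doses for several patterns of doses missed during titration, and no precedence is stated. Per participant the difference is 2 mg in most patterns and 4 mg in one pattern of one or two misses (6 mg arm, Weeks 2-3). It is a 4-week delay in reaching 6 mg when Weeks 1-3 are missed and titration restarts at Week 4. How many participants this touches cannot be estimated.

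The conclusion assumes that the week fixes the dose in Table 2, that no dose was taken late, and that Section 7.1.3 is followed where it permits a restart.

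Severity is moderate: a safety and consistency issue. A reader might infer that the primary result is compromised, but no effect on the primary endpoint is shown. The SAP (Sections 1.1, 1.6 and 2.4) records early termination and keeps efficacy descriptive, with safety among the remaining focuses. No view is taken here on which dose is right.

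**What to change.** Reconcile Table 2, Section 6.6 and Section 7.1.3 so that one stated rule governs doses missed before the assigned dose is reached, with cross-references between them. State how escalation continues after a restart. Make the Week 4 statements in Table 2 and Section 6.6 consistent with whatever rule is adopted. Confirm that blinded kit supply through the IRT can deliver that rule without the site knowing the strength. The choice of dosing rule is the sponsor's.

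The cost is protocol wording, a check or change of kit allocation, and possibly a few extra titration kits. No extra visits or participants are needed.

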7.2 PARTICIPANT DISCONTINUATION/WITHDRAWAL FROM THE STUDY

A participant may withdraw from the study at any time at his/her own request, or may be withdrawn at any time at the discretion of the Investigator for safety, behavioral, compliance, or administrative reasons.

If the participant withdraws consent for disclosure of future information, the Sponsor may retain and continue to use any data collected before such a withdrawal of consent.

If a participant withdraws from the study, he/she may request destruction of any samples taken and not tested, and the Investigator must document this in the site study records.

Refer to the SoA ([Section 1.3](#)) for data to be collected at the time of study discontinuation and follow-up and for any further evaluations that need to be completed.

All study withdrawals should be recorded by the Investigator in the appropriate screens of the eCRF and in the participant's medical records. In the medical record, at least the date of the withdrawal and the reason should be documented.

Participants who have withdrawn from the study cannot be rerandomized (treated) in the study. Their inclusion and randomization numbers must not be reused.

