9.3 POPULATIONS FOR ANALYSES

For purposes of analysis, the following populations are defined (Table 4):

Table 4 - Populations for analyses

Population	Description
Screened	All participants who sign the ICF.
Randomized	All screened participants who have a treatment kit number allocated and recorded in the IRT database, regardless of whether the treatment kit was used or not.
ITT	All participants randomized irrespective of rescue therapy use and compliance with the study protocol and procedures. Participants will be analyzed in the treatment group to which they are randomly assigned.
Safety	All participants randomly assigned to IMP and who take at least 1 dose of IMP. Participants will be analyzed according to the treatment they actually received.
ADA	All participants from the safety population with at least 1 postbaseline valid ADA sample after drug administration.
PK	All participants from the safety population with at least 1 valid PK sample available for analysis.

ADA: anti-drug antibody; ICF: informed consent form; IRT: interactive response technology; ITT: intent-to-treat; PK: pharmacokinetic

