9.4.1 Efficacy analyses

Table 5 - Efficacy analyses

Endpoint	Statistical Analysis Methods
Primary Change from baseline to Week 30 in HbA1c	
Primary analysis:
 
The primary efficacy endpoint will be analyzed using all HbA1c values measured at baseline and Week 30 (observed or imputed), regardless of treatment discontinuation or initiation of rescue therapy.
 
The primary analysis method for the primary efficacy endpoint will be an ANCOVA model with missing values imputed by MI analysis methods in 2 parts as follows:
 
 1. Missing endpoint data for participants who prematurely discontinue the IMP before the endpoint visit will be imputed using a model estimated from the participants in the same treatment arm who prematurely discontinue the IMP before the endpoint visit but have the measurement for the endpoint (retrieved dropouts). Considering that the number of participants in each treatment arm who discontinue the IMP but have the measurement for the endpoint is expected to be small, we propose to use a simple imputation model, where only the baseline measurements are included as the predictor. Each treatment group will have their own imputation model. Missing data will be imputed using the regression method.

Endpoint**Statistical Analysis Methods**

2. Missing endpoint data in all participants, including those in the efpeglenatide groups, who stay on the IMP until the endpoint visit will be imputed separately, using a model estimated from participant in the placebo group who stay on the IMP until the endpoint visit and have the endpoint data available. The imputation model will include the randomization strata (screening HbA1c [$<8\%$, $\geq 8\%$], SU use at screening [Yes/No]), and baseline HbA1c value. Missing data will be imputed using the regression method.

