#### **2.3.1.1 *Intent-to-treat population***

The ITT population is defined as all randomized participants, irrespective of rescue therapy use and compliance with the study protocol and procedures analyzed according to the treatment group allocated by randomization.

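### Protocol Section 7.2 lets the Investigator end study follow-up for compliance or behavior, at odds with the aim of collecting Week 30 data on every participant, on or off IMP

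*Protocol*

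**What the plan says.** Protocol Section 7.2 deals with leaving the study. Besides withdrawal at the participant's own request, it says that a participant "may be withdrawn at any time at the discretion of the Investigator for safety, behavioral, compliance, or administrative reasons". Nothing there confines the compliance or behavioral grounds to stopping IMP. For data collection it refers to the Schedule of Activities (SoA).

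Other parts of the plan point the other way:

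- Protocol 7.1, on stopping IMP: "In any case, the participant should remain in the study as long as possible to collect endpoint data at Week 30".
- Protocol 7.1.1: "As all data until the scheduled date of study completion will be used in statistical analyses, it is important to collect data for all participants". It then warns: "A high rate of missing data could jeopardize efficacy results of the study". For participants who stop IMP permanently it adds: "Every effort should be made to maintain participants in the study".
- Protocol 9.3 defines ITT as "All participants randomized irrespective of rescue therapy use and compliance with the study protocol and procedures". SAP 2.3.1.1 agrees: "irrespective of rescue therapy use and compliance with the study protocol and procedures analyzed according to the treatment group allocated by randomization".
- Protocol 9.4.1 bases the primary analysis on HbA1c values "measured at baseline and Week 30 (observed or imputed), regardless of treatment discontinuation or initiation of rescue therapy".

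Footnote a of the SoA (Protocol 1.3) asks for the Week 30 efficacy assessments in the context of premature permanent IMP discontinuation. For participants who themselves wish to leave, it asks for a safety visit about 6 weeks after the last dose and a contact around Week 30 about safety or survival status. It names no Week 30 HbA1c for them, and it does not mention participants whom the Investigator withdraws.

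**The concern.** The retention text is written for people who stop IMP. The withdrawal text gives the Investigator a separate route that ends follow-up altogether, on grounds that the ITT definition says should not matter. Non-compliance arises after randomization and can be linked to tolerability or to poor response. Protocol 4.3 describes nausea and vomiting as apparently dose-related. Protocol 6.1.2.2 has the Investigator check compliance once an FPG or HbA1c value is confirmed above the rescue threshold. Removal on compliance grounds could therefore follow a poor outcome, or differ between arms.

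Two things are at stake. One is avoidable missing Week 30 data. The other is the pool of retrieved dropouts (participants off IMP who still have a Week 30 value), on which the first part of the planned multiple imputation (MI) depends and which the protocol already expects to be small.

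**Working it through.** **1. The plan's own figure.** Inputs from Protocol 9.2: 160 per arm, difference 0.6, SD 1.1, two-sided alpha 0.05. Power = Φ(δ / (σ√(2/n)) − 1.96).

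- n = 160, δ = 0.6: 0.6 / (1.1 × √(2/160)) = 4.88, so power is 99.8% (stated: above 99%).
- n = 80, δ = 0.6: 93.2%, or 92.9% with the noncentral t (stated: 92%).
- n = 80, δ = 0.5: 82.0%, or 81.5% with the noncentral t (stated: 81%).

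The stated powers reproduce to within about 1 point. They use the full 160 and 80 per arm, and no allowance for missing data is stated.

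**2. The rules side by side.**

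| Situation | Week 30 efficacy data sought? | Source |
|---|---|---|
| Stops IMP, stays in study | Yes, every effort | Protocol 7.1, 7.1.1, SoA footnote a |
| Chooses to leave the study | Safety visit and Week 30 status contact only | SoA footnote a |
| Withdrawn by Investigator for compliance or behavior | Nothing specific | Protocol 7.2 |

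Non-compliance is not named in 7.1.1 among the reasons to stop IMP, yet 7.2 names it as a reason to leave the study. After baseline, HbA1c is scheduled only at Weeks 12 and 30, so an early leaver will usually have no endpoint value.

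**3. Effect on the planned imputation.** MI part 1 (Protocol 9.4.1) imputes for participants off IMP from same-arm retrieved dropouts. Leaving the study normally ends IMP too, so each such withdrawal adds one value to impute and removes one possible donor. With fewer than 5 donors in any arm, the whole primary analysis moves to the placebo-based back-up method. An arm with exactly 5 drops to 4 through a single such loss.

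**4. Effect on power, with assumed missing rates.** The documents give none, so take a share m = 5%, 10% or 20% per arm with no Week 30 value for any reason (noncentral t).

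| m | Completers per arm | Completer power, δ = 0.6 | Effect if active missing values are imputed as placebo, 0.6 × (1 − m) | Power at 160 per arm for that effect |
|---|---|---|---|---|
| 5% | 152 | 99.7% | 0.57 | 99.6% |
| 10% | 144 | 99.6% | 0.54 | 99.2% |
| 20% | 128 | 99.2% | 0.48 | 97.3% |

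In the background-therapy subgroups (80 per arm), completer power falls to 91.6%, 90.2% and 86.5% for 0.6, and to 79.5%, 77.3% and 72.3% for 0.5. Overall power is hardly touched; subgroup precision suffers more.

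**5. Effect on an observed-case mean.** Let a share p be withdrawn, with mean change worse by g than in those kept (mean R). The full-arm mean is (1 − p)R + p(R + g) = R + pg, and the observed mean is R, so the bias is p × g. Assume p = 2% to 10% (3.2 to 16 of 160) and g = 0.3 to 1.0 points: 0.02 × 0.3 = 0.006, up to 0.10 × 1.0 = 0.10 points. This is for one arm's mean. The bias in a between-arm difference is the difference of the two arms' values.

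**6. What the SAP now does.** SAP 1.6 and 2.4 drop the planned efficacy evaluations after early termination and leave descriptive summaries, generally on observed cases. SAP 2.5.4 accepts an early-termination value within 30 days of Day 210 (7 days for FPG), so a late leaver's HbA1c can still count between Days 180 and 240. SAP 2.5.3 leaves participants with missing data out of percentages unless otherwise specified.

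**The case against.** The case on the other side is substantial. ITT defines who is analysed and in which arm, so a withdrawn participant stays in it, and the endpoint may be observed or imputed. Retention in 7.1 and 7.1.1 is an aim, and 7.2 gives a discretion, so a colleague could call this loose drafting. Protocol 9.4.1 plans MI, a tipping-point analysis, a control-based analysis and a table of missing-data patterns, all aimed at non-random loss. Investigators are blinded to arm and to post-baseline HbA1c and FPG (Protocol 6.3.1). The response to poor compliance in 6.1.2.2 is corrective, not removal. The trial was terminated early and no confirmatory test remains.

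Most of this stands, and it limits the consequence. It does not remove the gap: imputation is a second-best remedy for data that could have been collected, and part 1 is weakened by the same loss. Blinding is not complete insulation, since Investigators receive threshold alerts and review self-monitored glucose.

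Three stronger readings are tempting but unsupported:

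- A reader might infer that outcome-driven removal would happen. The documents only leave it possible.
- A reader might set 0.10 against the 0.6-point design difference and report a 17% bias in the treatment effect (0.10 / 0.6). That needs the top of two assumed ranges and loss in one arm only. Loss in both arms would partly cancel, and 0.6 was set for a comparison planned with imputation.
- A reader might infer that every Investigator ground except unsafe procedures should go. The administrative ground is needed for the study and site closure allowed in Protocol 10.1.8, and the safety ground is a clinical matter that this point does not touch.

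**Conclusion.** The point holds as an internal inconsistency that is cheap to remove. Section 7.2 permits follow-up to end for compliance or behavior, although the rest of the plan wants Week 30 data irrespective of both, and no passage secures a Week 30 HbA1c for those removed. The result is avoidable and possibly outcome-related missing data, and a smaller donor pool for MI part 1.

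Its size is unknown because no withdrawal rate is given. The bias range in the working rests wholly on the assumed shares and gaps. Overall power would have stayed at 97% or more under the assumed missing rates. After early termination, the only efficacy output affected is the descriptive observed-case summaries, so no confirmatory conclusion depends on it.

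**What to change.** In Protocol 7.2, state that non-compliance or behavior alone does not end study follow-up. Such participants are followed under 7.1.1, at minimum for Week 30 HbA1c, FPG and body weight, unless consent to follow-up is withdrawn or attendance is not feasible. Leave the safety ground, the administrative ground (including study or site closure) and all rules on stopping IMP as they are.

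The cost is a sentence or two of protocol text, and sites continue to see a few less cooperative participants for the Week 30 visit. As this trial has stopped, new wording cannot recover data. SAP 2.2 already tabulates reasons for study discontinuation by treatment group, and that table should be read beside the observed-case efficacy summaries.
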